4.1 IPE Design

Whilst the impact evaluation will test the effectiveness of the financial incentive scheme, the implementation and process evaluation (IPE) will identify why and how the intervention achieves - or fails to achieve - the expected outcomes in relation to the Theory of Change (ToC).⁶⁸ It will also explore potential desirable and undesirable unintended consequences.69

Following best-practice guidance from the Medical Research Council (MRC),⁷⁰ BIT will conduct a mixed-methods IPE to understand issues relating to the (i) reach of the intervention, (ii) engagement with the intervention, (iii) mechanisms of impact, (iv) and implementation and feasibility.

This mixed-methods approach will incorporate qualitative data from interviews and focus groups and quantitative data from routinely collected in-app user metrics. Using multiple data sources, BIT will enable DHSC to:

- Gain broad insights across a large number of individuals: the quantitative • IPE will assess key process variables (e.g., engagement with the app) and generate evidence on the mechanisms of impact hypothesised in the ToC.
- Develop an in-depth understanding of individual experiences: qualitative methods will further enrich the IPE by generating in-depth insights into the range and diversity of the experiences of different stakeholders.

The methods used for the IPE will be (i) rooted in the details of the Theory of Change and the user journey (Figure 2), (ii) mindful of the needs of the research participants, especially those from underserved communities, and (iii) form part of an integrated plan with the impact evaluation, so that the analysis from the IPE can help to explain any significant or null effects observed.

In the sections that follow, we outline the core research questions for both the gualitative and guantitative IPE (4.1.1), and then describe the methodology for the quantitative (Section 4.2) and the qualitative IPE (Section 4.3).

4.1.1 Research questions

Core research questions

In line with the MRC's recommendations, BIT used the causal hypotheses outlined in the Theory of Change (see accompanying Intervention design & ToC document) and

⁶⁹Public Health England. (2018). *Guidance: Process Evaluation*. Retrieved from

⁶⁸ For the ToC, please see the complementary document.

www.gov.uk/government/publications/evaluation-in-health-and-well-being-overview/process-evaluation ⁷⁰ Moore G. F., Audrey, S., Barker, M., Bond, L., Bonell, C., Hardeman, W. et al. Process evaluation of complex interventions: Medical Research Council guidance BMJ 2015; 350 :h1258 doi:10.1136/bmj.h1258

user journey (Figure 2 in the Intervention design & ToC document) to prioritise research topics for investigation.⁷¹ These are:

- **Reach**: what factors affected the intervention's reach?
- **Engagement**: what factors affected the engagement of users with the intervention?
- **Mechanisms of impact**: through what mechanisms does the intervention affect behaviour change?
- Implementation and feasibility: how was the intervention implemented and is it scalable?

Table 14 below provides a summary of the high-level research questions for each topic along with the IPE methodology to be employed. As noted, a more detailed breakdown of the quantitative and qualitative methodology are outlined in Sections 4.2 and 4.3 respectively.

Research Topic	Resea	rch question	IPE	Methodology
Reach What factors affected the intervention's	t factors participants?		Quant	Descriptive analysis of metrics from marketing campaign and in-app
reach?	1.2	What are the characteristics of intervention recipients?		engagement (summary statistics)
	1.3	What was the role of marketing and communications in motivating participants to join the intervention?	Qual	Thematic analysis of interviews and focus groups with recipients and non-recipients.
	1.4	What were the channels of reach and how did they affect sign-up?		and non-recipients.
	1.5	How is the intervention perceived by recipients, and non-recipients of the financial incentives?		
	1.6	What are the barriers and facilitators to the intervention's reach?		
Engagement What factors affected the	2.1	To what extent does the intervention engage participants?	Quant	i. Descriptive analysis of in-app
engagement of users with the intervention?	2.2	What are the characteristics of those who engage with the intervention for the duration of the trial, those who partly engage, and those who disengage?		engagement metrics and participant demographics (summary statistics) ii. Regression analysis of in-app engagement metrics and participant demographics

Table 14. Summar	v of research topics.	research questions	and methodologies.
	y or rooodron coproo,	1000001011 900000010110	ana mouroaologioo.

⁷¹ Moore G. F., Audrey, S., Barker, M., Bond, L., Bonell, C., Hardeman, W. et al. Process evaluation of complex interventions: Medical Research Council guidance BMJ 2015; 350 :h1258 doi:10.1136/bmj.h1258

	2.3	In what ways did users engage with the app after signing up?		Descriptive analysis of in-app engagement metrics (summary statistics)
			Qual	Thematic analysis of interviews and focus
	2.4	What were participants' experiences and perspectives of intervention?	Qual	groups with recipients and non-recipients.
	2.5	What are the barriers and facilitators to engagement with the intervention?		
Mechanisms of impact Through what mechanisms	3.1	To what extent do incentives affect in-app engagement?	Quant	Regression analysis of treatment impact on in-app engagement metrics
does the intervention affect behaviour change?	3.2	What barriers and facilitators - both contextual and individual - affect the extent to which the intervention changes behaviours for recipients and non-recipients of the financial incentives?	Qual	i. Thematic analysis of interviews and focus groups with recipients and non-recipients
	3.3 How do features of the incentive scheme affect (or not) the extent to which the scheme changes behaviours?		Qual	 ii. Thematic analysis of focus groups with delivery and reward partners
Implementatio n and feasibility How	4.1	What was the process for developing and implementing the intervention among delivery and reward partners?	Qual	Thematic analysis of focus groups with delivery and reward
was the programme implemented	4.2	Are the design and delivery processes fit for scaling and sustaining the intervention?	Qual	partners.
and is it scalable?	4.3	How was the intervention implemented?	Qual	
	4.4	What are the facilitators and barriers to scaling and sustaining the intervention (including financial incentives) beyond the pilot?	Qual	
	4.5	What was the extent of 'gaming' and data errors in the intervention?	Quant	Descriptive analysis of in-app data on inconsistencies and outlying behaviour (summary statistics)

Using qualitative methods (outlined in section 4.3), BIT will also explore how acceptability, contextual factors and barriers/facilitators to the implementation and outcomes affect each research question to ensure that the IPE addresses all core components of the MRC's framework for process evaluations of complex interventions.⁷²

⁷² Moore G. F., Audrey, S., Barker, M., Bond, L., Bonell, C., Hardeman, W. et al. Process evaluation of complex interventions: Medical Research Council guidance BMJ 2015; 350 :h1258 doi:10.1136/bmj.h1258

4.1.2 Unintended consequences

The IPE will also explore potential unintended consequences of the intervention using qualitative methods. Unintended consequences may include *negative* or *harmful* outcomes (e.g. increased purchase of unhealthy foods given the increase in financial means) or *positive* or *helpful* "spillover" effects (e.g., increased self-reported wellbeing for those participating).

To identify unintended consequences, BIT:

- 1. Interrogated the Theory of Change: in partnership with HUL, BIT has already reviewed the ToC to identify potential unintended consequences both helpful and harmful. This involved testing the theoretical assumptions of the ToC and a systematic evaluation of the inputs, activities, outputs, outcomes and impact to generate a list of hypothesised unintended outcomes at each stage of the intervention. These were used to inform questions in the topic guide to surface unintended consequences.
- 2. Identified any "dark logic" underlying the Theory of Change: whilst the Theory of Change outlines a path to *positive* or helpful outcomes and unintended consequences, a "dark logic model" aims to anticipate plausible *negative* or harmful unintended consequences. BIT examined the Theory of Change and its assumptions to identify any "dark logic" that might result from the intervention, and used this to inform the topic guides.⁷³
- 3. Developed a sampling strategy and qualitative methodology that enables identification of unintended consequences: definitions of unintended consequences may differ between and within populations. BIT has developed a sampling strategy for the qualitative interviews and focus groups to capture the perspectives about negative unintended consequences from a wide range of population subgroups, not just those most likely to have benefitted.

⁷³ Bonell C., Jamal, F., Melendez-Torres, G.J., et al. 'Dark logic': theorising the harmful consequences of public health interventionsJ Epidemiol Community Health 2015;69:95-98.

4.2 Quantitative methods

Note: As specified in the previous versions of this protocol, we have updated the IPE in line with evolving information about the intervention and marketing design plan as well as information about data availability from HUL. This represents the final version of the quantitative IPE.

4.2.1 Methods overview

The quantitative IPE aims to:

- 1. Describe the intervention's reach and users' engagement
- 2. Test key mechanisms of action
- 3. Explore potential 'gaming' and data errors

Table 15 below summarises how the user journey stages map onto the planned quantitative IPE analyses.

User journey stage	Intervention step	Quant IPE analysis	Topic covered
Marketing campaign and acquisition	 Downloading app and in-app consent App usage 	Marketing reach, acquisition, and usage analysis	 Reach Engagement Mechanisms of action Implementation and feasibility
Onboarding	 Mandatory details completion Wearable device connection/use 	Engagement with the intervention and mechanisms of action	 Engagement Mechanisms of action Implementation and feasibility
	5. Intake24 completion	N/A ⁷⁴	N/A
	6. Health surveys	Engagement with the intervention and mechanisms of action	 Engagement Mechanisms of action Implementation and feasibility
	7. Randomisation	N/A ⁷⁵	N/A
Interaction with the intervention (continued app	 'New user journey' of app learning/engagement - first 30 days 	Engagement with the intervention and mechanisms of action	EngagementMechanisms of action
usage)	post-randomisation ⁷⁶ 9. Continued app usage across trial period (completing challenges,	Analysis of 'gaming' and data errors	 Implementation and feasibility

Table 15. Stages	s of user journey	and quantitative	IPE analyses
9	, , , , , , , , , , , , , , , , , , , ,		

⁷⁴ This data concerns the impact evaluation only and will be analysed as part of that.

⁷⁵ This data concerns the impact evaluation only and will be analysed as part of that.

⁷⁶ According to the HUL design plan, this includes: (i) Introduction to app features, (daily) mood check-ins and orientation, through email and push notifications; (ii) Prompts to participate in weekly health challenges focused on PA and nutrition habits; (iii) Survey invites, through push notifications and email – which act as part of the user experience as we are able to better tailor health insights and platform experience with this data; (iv) Milestone celebrations, points and rewards (for incentive groups) and NPS / feedback at 30-day mark. *This is specified here for additional context around the user journey; engagement in these activities will be measured by a set of metrics capturing in-app engagement across the intervention period.*

redeeming incentives etc.)		
-------------------------------	--	--

In line with the impact evaluation, one cross-cutting focus of the quantitative IPE will be understanding the experience and behaviours of the entire participant sample and of key participant subgroups. For subgroup analyses we will use the same population characteristics and cut offs as those specified for the impact evaluation.

The quantitative IPE makes an important distinction between **engagement with** *intervention components* (e.g. selecting and completing challenges, redeeming rewards), and **engagement with** *evaluation components* (e.g. completing Intake24 surveys). The quantitative IPE is focused on the former; the impact evaluation includes a focus on the latter, as part of attrition management.

The quantitative IPE will use a combination of descriptive analyses (summary statistics and data visualisation) and regression analyses.

4.2.2. Reach, acquisition, and usage analysis

The reach, acquisition, and usage analysis will focus on (i) quantifying the number of consenting users and breaking down this sample by relevant subgroups, (ii) quantifying the amount of engagement with the app during the duration of the pilot and exploring how engagement levels vary by study arm, (iii) identifying study-level and personal-level predictors of engagement with the app.

Table 16 describes the metrics that will be analysed. The feasibility of the planned analyses rely on HUL's ability to share the in-app metrics described in Table 16 with BIT, which has been confirmed by HUL.

Metric	Data source	Number of timepoints		Which subgroups
Number of consenting users recruited from launch until recruitment finishes (in N)	In-app data	1 (total timespan)	5	Total and by study arm
% of randomised adults that are very active users (defined as app installed and opened at least once over the course of 7 days) per week from randomisation to week 24 (in %)	In-app data	22 (weekly)	5	Total and by study arm
% of randomised adults that are churn-out users (defined as app not opened since more than 30 days from randomisation to week 24) (in %)	In-app data	22 (weekly)	5	Total and by study arm

Table 16	Motrico	undorlying	the reach	occuricition	and upper a	nalvoia
	weincs	unuenvinu	life reach	. accuuisillon.	and usage a	11012515
				,		

Number of consenting users from launch until recruitment finishes (in N), by subgroup	In-app data	1 (total timespan)		Total and by study arm. Each respectively by deprivation status (2 groups), ethnicity (5 groups), sex (3 groups), age (2 groups), baseline F&V intake (2 groups), baseline MVPA (2 groups).
---------------------------------------------------------------------------------------------	-------------	-----------------------	--	------------------------------------------------------------------------------------------------------------------------------------------------------------------------------------------------------------------------

The above metrics will be analysed descriptively using summary statistics.

Additionally, we will conduct a regression analysis to identify the factors predicting the proportion of intervention period during which consenting participants are categorised as being very active (defined as app installed and opened at least once over the course of the last 7 days). The factors explored in the regression will include:

- age,
- sex,
- baseline overweight/obesity status (BMI ≥ 25),
- ethnicity,
- deprivation status,
- disability status (self-reported presence or absence of physical or mental health conditions or illnesses lasting or expected to last 12 months or more categorised as yes, not, prefer not to say),
- education (degree or above; professional, vocational or other work-related qualifications; no qualification; prefer not to say)
- brand of wearable (Apple watch, Fitbit, Better Health fitness tracker), Garmin, others),
- study arm (control, low incentives, medium incentives, high incentives),
- baseline MVPA, and
- baseline fruit and vegetable intake.

The cut offs for each predictor will be defined following the same criteria used in the impact evaluation (unless specified above).

Estimated coefficients and statistical testing for the predictors will provide robust insights into whether overall in-app engagement differs by any demographics and baseline behaviours. The general equation for estimating the model is as below:

(4)
$$y_{ij} = \alpha + \beta Treatment_j + \gamma_X X_{ij} + u_{ij}$$

 $u_{ij} \sim N(0, \sigma_u^2)$ for all i, j

where

- y_{ij} is the proportion of weeks in the intervention period that participant *i* within household *j* is categorised as being very active;
- *Treatment* is a categorical variable for treatment group (the categories are control group, low incentives, medium incentives and high incentives, with the control group being the reference category);
- *X_{ij}* are individual level (including age, sex, ethnicity, education, disability status, baseline obesity status, baseline fruit and vegetable intake, baseline MVPA, and brand of wearable) and family level covariates (e.g. deprivation status) we will take missing values for these covariates as separate categories rather than imputing;
- u_{ij} is an idiosyncratic error term, which is assumed to follow a Normal distribution (denoted as *N*) of zero mean and a variance of σ_u^2 .

Taken together this analysis section will help to answer following questions:

- To what extent does the app reach participants?
- What are the characteristics of people taking up the programme?
- To what extent does the app engage participants?
- What characteristics predict participants' in-app engagement for the duration of the trial?
- To what extent do incentives affect in-app engagement?

We originally also planned to explore the marketing channels through which consenting participants were reached, but we will explore this through the qualitative IPE, as HUL informed us that this data will not be available.

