¹⁰ Note that a minimum of 4 valid days of physical activity data are required for inclusion in the evaluation. The first of the 5 days of data collected at baseline is therefore excluded from the evaluation as it is assumed to be a partial day. A valid day of data is one for which there is at least 6 hours of device wear time. This is explained in section 2.6 Data collection, management, and analysis ¹¹ BIT and HUL acknowledge that the risk of attracting too many users is also present. In this case, HUL will collect the same data as currently proposed during onboarding /registration (i.e. email, name, DOB, BMI, consent, gender etc) from the 'extra' users who will be invited to take part in the pilot. The app will limit the total number of registered users to 31,500. Once this number has been reached, users will see a message before they sign up, alerting them that the pilot is full and no more registrations are permitted, nor data captured.

¹² For the aim of the evaluation we do not consider the wearable a financial incentive (as part of the scheme), as the wearables will be provided to both the intervention and control group primarily to measure physical activity. Providing the wearable to both the intervention and control group will allow us to isolate the effects of providing financial rewards that are contingent on behaviour change. However, we acknowledge that users' behaviour will be affected by the presence of a wearable device.

Before the trial	Recruitment	Testing and fine-tuning of recruitment materials via UX research and online RCTs.	HUL, BIT supported with one online RCT
Before the trial	Baseline phase	Testing and fine-tuning the onboarding phase via UX and acceptability user testing research. This includes minimising the number of questions users are asked during the onboarding phase (for the evaluation and the fine-tuning of the scheme).	HUL
Before the trial	Baseline phase	Make data collection easy and attractive: (i) Adopt reminders to encourage data collection; (ii) Display the Intake24 survey link prominently on the 'to-do' list dashboard of the app when users open it so they'll see it every time they open the app regardless of the prompt; (iii) Encourage two recalls of Intake24 and wearing the device with a small payment (£5 as points); (iv) Provide feedback after each Intake24 recall	HUL
Before the trial (triggered)	Baseline phase	Extend the baseline phase to up to 2 weeks if users are slow to provide their data	HUL

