Before the trial	Onboarding phase	Adopt a flexible onboarding period for 'slow onboarding users' if needed - ideally a user completes screening in 2 or 3 weeks (nudged to do so), but if they don't, they enter the trial (randomisation) when they have met the baseline criteria, rather than after a predetermined window of time.	HUL
		The latest calendar date that a user can complete onboarding (pass screening) is the last day of the recruitment window.	
During the trial	Recruitment	Extend the recruitment period beyond 6 weeks if necessary	HUL
During the trial (triggered at M5)	Trial period	Make data collection attractive: Consider encouraging wearing and syncing the wearable device with the app in the crucial data collection weeks at m3 and m5 with a small payment (£10), if attrition is deemed relatively too high ¹³ at the data collection point at m1 and m3.	HUL
During the trial (triggered at M3 and M5)	Trial period	Make data collection attractive: Consider encouraging filling in Intake24 at m3 and m5 with a larger payment (£10), if attrition is	HUL

¹³ We consider the attrition too high if the number of users not providing their data 10% smaller than expected at the start of the 1 month mark (see Table 6 for the expected attrition at different trial stages).

		deemed relatively too high ¹⁴ at the data collection point at m1. At m5 - for PA, users will receive £5 for syncing their fitness tracker (any amount of data > 0) during weeks 21 and 22 - up to 2 times so they can earn up to an extra £10.	
During the trial (triggered)	Trial period	Extend the data collection window from 2 to 3 weeks (21 days) at m3 and m5 for all measures (i.e. Intake24, steps, WHO5, sleep and weight)	HUL
During the trial	Trial period	Pull data collection forward. Change M5 data collection window to start earlier i.e. during the 20th week (day 134 to day 155).	HUL
After the trial	Recruitment and baseline phase	Shift the focus of the evaluation to a shorter follow-up (e.g. after 3 months of treatment instead of 5 months). If the sample size at 5m is less than 80% of the total sample size (n = 4,200) that the trial requires in order to detect a minimum effect size for primary outcomes (see Table 7 for details), we will use data from the 3m mark instead of the 5m mark in the analysis. ¹⁵	BIT

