Baseline period	Day 1 of baseline: users are invited to provide their first recall. Users are informed that the first two recalls they will provide (to be provided on two separate days, including information about weight) will be remunerated with a payment of £5 each in points. The second intake24 is optional; users are encouraged to complete the second one within 3 days. The survey will be prominently displayed on the dashboard of the app when users open it for the full duration of the baseline period.	If a user owns a wearable device, they are encouraged to sync their own device with the app and provide their PA data from the first day of the baseline period. If a user orders a wearable device, they are encouraged to sync it with the app and provide their PA data as soon as they receive the device. Users will be nudged for the full duration of their baseline period to wear the device and periodically sync it with the app. In the analysis, we will use all valid daily PA data provided during the baseline period (valid = device worn for at least 6h)
1 month mark (starting the 5th week after randomisation)	 Day 1: users are invited to provide a recall. Users are informed that the first two recalls they provide in the following two weeks will be remunerated with a payment of £5 each in points. Reminders, feedback and survey prominence are repeated as per the baseline phase. In the analysis, we will use all recalls submitted during the 5th and 6th week after randomisation for the 1m mark. 	In the 5th week after randomisation, users will be nudged to wear the device as long as possible for 7 days and sync the device with the app. In the analysis, we will use all valid daily PA data provided during the 5th week after randomisation for the 1m mark. If there are missing values in that week, we will impute them with valid values (if available) on the same day of the week within 2 adjacent weeks (i.e. weeks 3-7).

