	Eligibility	Full postcode	Yes	To select eligible participants, and to merge postcode-level deprivation data with GUIDs	N/A
	Eligibility	Resident of Wolverhampton	Yes	To select eligible participants	Yes; No
Uptake and	Wearable use	Daily wear time	Yes	For imputation of missing values	0~24 hours
Engagement	App use	Whether a GUID opens the app by day	Yes	To infer active user status and attrition	Used to identify different types of users: Very active users: app installed and opened at least once over the course of 7 days Active users (Users who have opened the app at least once in the last 30 days). Inactive users (Users who have not opened the app in 30 days)

Table 10. Illustrative structure of data fields to be collected by HUL and to be transferred to BIT

			Churn outs (Users who have not open the app for more than 30 days)
App open date	Yes	To examine wear time / app opens for the same GUID over time	N/A

[figure not shown]

Figure 3. High-level user journey for participants, from an evaluation point of view.

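### The any-opening outcome of equation (4) also counts app openings made only for paid dietary recalls, so part of an arm difference may be evaluation response rather than use of the intervention

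*Protocol*

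**What the plan says.** Protocol section 4.2.1 separates engagement with intervention components (challenges, rewards) from engagement with evaluation components (Intake24). It then states: "The quantitative IPE is focused on the former; the impact evaluation includes a focus on the latter, as part of attrition management". Table 15 in the same section marks Intake24 completion as not applicable to the quantitative process evaluation, and its footnote assigns those data to the impact evaluation.

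Section 4.2.2 describes its own aim as "quantifying the amount of engagement with the app during the duration of the pilot and exploring how engagement levels vary by study arm". Table 16 reports the weekly percentage of very active users by arm. Equation (4) regresses, on arm and covariates, the proportion of weeks in which a participant is "categorised as being very active (defined as app installed and opened at least once over the course of the last 7 days". Among the questions the section is meant to help answer is "To what extent do incentives affect in-app engagement". The field listed in Table 10 is "Whether a GUID opens the app by day", a daily yes/no.

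On recalls, Table 2 (section 2.2.3) plans to "Display the Intake24 survey link prominently on the 'to-do' list dashboard of the app when users open it". Table 9 (section 2.6.1.1) says of the baseline recall: "The survey will be prominently displayed on the dashboard of the app when users open it". It repeats the reminders and survey prominence at follow-up. The first two recalls in each window earn £5 each in points, or £10 each at 3 and 5 months if the mitigation is triggered. The recall windows are weeks 5-6, 13-14 and 21-22, widening to weeks 13-15 and 20-22 under mitigation.

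**The concern.** A user who opens the app only to reach a paid recall is scored as very active for that week, although section 4.2.1 places this activity outside the process evaluation. Nothing in section 4.2.2 leaves out the measurement weeks.

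This would matter little if recall completion were equal across arms, but the protocol expects otherwise. Table 6 plans higher attrition in control, and section 2.6.3.1 provides inverse probability weighting for that difference. The impact evaluation thus treats differential response as a source of bias, while equation (4) adds it to engagement. Question 3.1 sits under mechanisms of impact in Table 14, so an arm coefficient fed partly by recall completion could be taken as evidence for a mechanism it does not measure. The weekly very-active curves may also rise at the measurement windows because of the trial's own reminders and payments.

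**Working it through.** **Inputs (Table 6, section 2.4.2.3).** Number randomised, then attrition at 1, 3 and 5 months:

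| Arm | N | 1m | 3m | 5m |
|---|---|---|---|---|
| High | 1,900 | 18% | 44% | 62% |
| Medium | 1,950 | 18% | 45% | 63% |
| Low | 2,250 | 21% | 50% | 69% |
| Control | 9,400 | 26% | 60% | 78% |

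**Step 1: reproduce Table 6.** Summing N × (1 − attrition) over arms gives 11,890 at 1 month (stated ~11,900), 7,022 at 3 months (~7,100) and 4,209 at 5 months (4,200). The table is reproduced to within rounding.

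**Step 2: the artefact.** Suppose responders open the app only for recalls and nobody uses the intervention. The equation (4) outcome in an arm is then the sum over windows of (opening weeks in window × response rate), divided by the weeks in the period. Response is taken as 1 − attrition and the period as 24 weeks.

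*One opening week per window:*
- Control: (0.74 + 0.40 + 0.22)/24 = 1.36/24 = 5.67%
- High: (0.82 + 0.56 + 0.38)/24 = 1.76/24 = 7.33%
- Medium: (0.82 + 0.55 + 0.37)/24 = 1.74/24 = 7.25%
- Low: (0.79 + 0.50 + 0.31)/24 = 1.60/24 = 6.67%
- Pooled numerator: (1,900×1.76 + 1,950×1.74 + 2,250×1.60)/6,100 = 1.695
- Pooled gap: (1.695 − 1.36)/24 = **1.4 points**

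*Two opening weeks per window (6 of 24 weeks):* every figure doubles. The pooled gap is **2.8 points** (high 3.3, medium 3.2, low 2.0).

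*Mitigation windows of 2, 3 and 3 weeks, app opened in every one (8 of 24 weeks):*
- Control: (2×0.74 + 3×0.40 + 3×0.22)/24 = 3.34/24 = 13.92%
- High 4.46/24 = 18.58%; medium 4.40/24 = 18.33%; low 4.01/24 = 16.71%
- Pooled gap: **3.9 points**

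Table 16 lists 22 weekly timepoints. With 22 as the denominator the pooled gaps are 1.5, 3.0 and 4.3 points.

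**Step 3: would it show?** The protocol gives no SD for this outcome. Assuming two-sided alpha 0.05 and ignoring household clustering, the chance that high versus control is significant on the artefact alone (24-week period) is:

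| Opening weeks per window | SD 0.20 | SD 0.30 | SD 0.45 |
|---|---|---|---|
| One | 0.91 | 0.60 | 0.31 |
| Two | 1.00 | 0.99 | 0.84 |

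**Step 4: direction of the bound.** A responder who would have opened the app that week anyway adds nothing. The gaps are therefore upper bounds, provided such other openings are at least as common among responders in the incentive arms as in control, which is the natural expectation.

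**The case against.** The strongest reply is that section 4.2.2 speaks of engagement with the app and measures exactly that. Section 4.2.3 handles components separately: Table 17 reports challenges selected and completed, points and rewards by arm, and equation (5) is a second regression by arm. Table 14 answers question 3.1 with engagement metrics in the plural. This stands so far as it goes: the protocol names no main process outcome, and equation (4) is one of two regression outcomes. It does not remove the mismatch, because section 4.2.2 falls under the scope set in 4.2.1.

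A reader might infer that the arm difference would be spurious. The documents do not support that. Arms are randomised and the recall payments carry no arm restriction, so a difference in openings is a real effect of the offer on openings. Only its label is at issue.

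A reader might also extend the complaint to syncing and all in-app surveys. That goes too far. The payment under which "users will receive £5 for syncing their fitness tracker (any amount of data > 0) during weeks 21 and 22" is a 5-month measure within a triggered mitigation. Syncing also supplies the data behind the physical activity challenges, and the protocol does not say that it requires opening the app. Table 15 places health surveys under engagement with the intervention, and a footnote to it counts survey invitations as part of the user experience. Only Intake24 recalls clearly fall outside the stated scope.

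Finally, section 2.6.3.2 encourages both recalls in the same week, so the two- and three-week scenarios are ceilings rather than expectations.

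**Conclusion.** The point holds in a limited form. The equation (4) outcome and the weekly very-active metric count openings that the plan's own scope excludes, and the plan expects those openings to be rarer in control. On Table 6 rates, this alone could produce a pooled gap of about 1.4 points, with ceilings of about 2.8 or 3.9 points depending on window length.

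The figures assume that Table 6 attrition stands for recall response, that responders open the app for nothing else in those weeks, and a 24-week period. Statistical significance is plausible but not assured, since the SDs are assumptions. No primary or secondary trial outcome is affected. The estimate is valid for app opening; what it cannot support unaided is a statement about engagement with the intervention.

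**What to change.** Keep the any-opening version of equation (4), label it general app use, and mark the data-collection windows on the weekly plots. Also estimate equation (4) over the weeks outside those windows: omit weeks 5-6, 13-14 and 21-22, or weeks 5-6, 13-15 and 20-22 if the mitigation windows apply. Base the conclusion for question 3.1 about engagement with the intervention on that version together with the component metrics in Table 17.

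Do not define an active week by reward redemption. Section 2.5.1 says control users are not rewarded with incentives, so such a definition would differ by arm by construction. Recalls are paid in points, so state whether those points enter the points-earned metrics before relying on them.

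The cost is small: a wording change and a recode of daily app-opening data already due to be shared. The added version uses 18 of 24 weeks, or 16 under mitigation, and so discards some genuine use in the omitted weeks.
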